**3.2 Secondary Endpoint(s)/Event(s)/Outcome(s):**

**3.3** There will be 7 secondary endpoints:

- To ensure losartan is safe and well tolerated in hospitalized patients with COVID-19, we will:
  - Compare daily hypotensive episodes (MAP < 65 mmHg) prompting intervention (indicated by a fluid bolus  $\geq 500$  mL)
  - Hypotensive episodes requiring intervention (vasopressors or fluid bolus)
  - Determine the incidence of new or worsening renal failure

- Daily Sequential Organ Failure Assessment (SOFA) score to day 10. If data are unavailable for any given organ failure, we will use the last value carried forward approach.
- Change in estimated P/F ratio daily between groups
- In-hospital, 28, and 90-day mortality (by using state death certificate or social security death index data)
- Resource utilization as assessed by: ICU admission, ventilator free days, oxygen free days, vasopressor free days, ICU and hospital length of stay
- Respiratory failure as measured by the utilization of Bilevel Positive Airway Pressure (BiPAP), high flow nasal cannula, mechanical ventilation or extracorporeal membranous oxygenation (ECMO) utilization, as well as trends in S/F ratio.
- Symptomatic improvement as assessed by the dyspnea PROMIS and SF-12 assessments of dyspnea and functional status
- Percentage of subjects reporting each severity rating on the *7-point ordinal scale* [ Time Frame: Day 15 ]
  - The *7-point ordinal scale* is an assessment of the clinical status at the first assessment of a given study day. The scale is as follows: 1) Death; 2) Hospitalized, on invasive mechanical ventilation or extracorporeal membrane oxygenation (ECMO); 3) Hospitalized, on non-invasive ventilation or high flow oxygen devices; 4) Hospitalized, requiring supplemental oxygen; 5) Hospitalized, not requiring supplemental oxygen; 6) Not hospitalized, limitation on activities; 7) Not hospitalized, no limitations on activities.
  - Change in viral load (nasopharyngeal or oropharyngeal swab and blood)

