**3.4 Justification of the secondary outcomes:** Patients severely infected with respiratory dysfunction may be at increased risk of volume depletion, acute kidney injury, or the development of hypotension, so we will systematically track these measured instead of relying upon adverse event reporting which introduces the potential for bias. We will measure P/F ratios daily in case our choice of 7 days proves incorrect. SOFA score is a validated measuring of organ failure in critically ill populations that can be determined. Death is clinically important, but we do not believe our sample size is adequately powered to detect a difference in this outcome. Resource utilization and respiratory support are critical in surge capacity situations and of relevance to this disease process. Validated study instruments to assess dyspnea and physical function will assess patient-centered outcomes and strengthen the biologic plausibility of the intervention. The 7-point ordinal scale described is used by other ongoing Covid-19 clinical trials and will allow harmonization of the trial results. Changes in viral load are important to assess the theoretical possibility of losartan induced ACE2 expression leading to increased viral entry, propagation, and shedding.

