Study site personnel must alert a study investigator of any serious and study drug or study procedure related adverse event within 24 hours of investigator awareness of the event. Alerts issued via telephone are to be immediately followed with official notification on the adverse event case report form.

All AEs that do not meet any of the criteria for serious should be regarded as non-serious AEs.

- **Preexisting Condition:** A preexisting condition is one that is present at the start of the study. A preexisting condition will be recorded as an AE if the frequency, intensity, or the character of the condition worsens during the study period.

- **Post-study Adverse Event:** All unresolved AEs will be followed by the Investigator until the events are resolved, the subject is lost to follow-up, or the AE is otherwise explained. At the last scheduled visit, study personnel will instruct each subject to report any subsequent event(s) within 3 months of study completion that the subject, or the subject's personal physician, believes might reasonably be related to participation in this study.

- ***Abnormal Laboratory Values:*** A clinical laboratory abnormality should be documented as an AE if any 1 of the following conditions is met:
  - The abnormality suggests a disease and/or organ toxicity that worsened from the time of enrollment, or
  - The abnormality is of a degree that requires active management; e.g., change of dose, discontinuation of the drug, more frequent follow-up assessments, further diagnostic investigation, etc.
- ***Continuous SAEs of interest monitoring:*** The following SAEs will be continuously reported to the DSMB: deaths. Cardiovascular events (need for vasoactive drugs or fluids for hypotension), and respiratory events (worsening hypoxia, worsening acute respiratory distress syndrome, or new respiratory failure) will be continuously reported to the DSMB within 24 hours of recognition for safety reasons. While they will be reported continuously, they will not necessarily be filed as SAEs unless the investigator deems it to be related to study procedures (see below)

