- ***Other outcomes that may be exempt from adverse event reporting:*** Study specific outcomes as outlined in 5.1 and 5.2 are exempt from adverse event reporting unless the investigator deems the event to be related to the study procedures (or of uncertain relationship) or if the event leads to discontinuation of study procedures. The following are examples of events that will be considered study specific clinical outcomes and will be systematically tracked through the study design. The rationale for this criteria is that these events are likely to be present in a large proportion of the study population, and relatedness will be subject to significant subjective assessment, making adverse event reporting can be sporadic and inconsistent. Therefore, events more likely to be truly related to a study intervention are better treated by consistent tracking through the systemic design and collection of potentially related adverse events:
  - Respiratory events: decreased PaO2/FiO2, hypoxia, worsening acute respiratory distress syndrome, or respiratory failure.
  - Cardiovascular events: (need for vasoactive drugs or fluids for hypotension)
  - Hepatic events: hepatic injury or liver dysfunction that leads to an increase from baseline in the serum level of bilirubin.
  - Renal events: renal failure, renal insufficiency, or renal injury that leads to an increase from baseline in serum creatinine.
  - Hematologic/coagulation events: coagulopathy, disseminated intravascular coagulation, thrombocytopenia, or thrombocytosis.
  - Changes in serum sodium and potassium
- ***Scales Used to Grade Severity of Adverse Events:*** All AEs will be graded in the following manner:
  - Grade 1 (Mild): Events require minimal or no treatment and do not interfere with the participant's daily activities.
  - Grade 2 (Moderate): Events result in a low level of inconvenience or concern. Moderate events may cause some interference with functioning.

- Grade 3 (Severe): Events interrupt a participant's usual daily activity and may require systemic drug therapy or other treatment. Severe events are usually incapacitating.
- Grade 4 (Life-threatening): Any adverse drug experience that places the participant, in the view of the Investigator, at immediate risk of death from the reaction as it occurred (i.e., it does not include a reaction that had it occurred in a more severe form, might have caused death).
- Grade 5 (Death)

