- **Response to possibly, probably, or definitely related AEs and SAEs:** SAEs determined to be probably or definitely related will prompt discontinuation of study drug. AEs determined to be probably or definitely related with prompt a) decrease in study drug from twice a day to once a day if currently dosing twice daily, b) discontinuation of study drug if only taking once daily, or c) discontinuation for study drug at the discretion of the investigator.
- **Anticipated Adverse Events:** Adverse events are not expected from any of the study procedures. We do not expect any serious adverse events due to losartan.
- **Recording and Documentation**
  - At each contact with the subject, personnel must seek information as to discomforts or adverse experiences by specific questioning and, as appropriate, by examination. This will typically occur via phone or telemedicine due to concerns regarding infectious contagion. Information about AEs to be recorded includes event description, time of onset, investigator assessment of severity, relationship to Study Agent(s)/Intervention(s), and time of resolution/stabilization of the event. All AEs occurring during the study period (from time of consent signing to study day 15) must be documented appropriately regardless of relationship to study products or procedures unless included on the list of clinical outcomes that may be exempt from adverse outcomes reporting as part of the study protocol and outcomes. Information on all identified AEs will be recorded within 5 days of recognition in the appropriate AE module of the case report form (CRF) on Redcap, and within 24 hours in the event of a SAE.

18.3 **Data Safety Monitoring:** A data safety monitoring board (DSMB) has been convened and includes 4 individuals meeting the key element criteria below, and includes a biostatistician with prior clinical trials DSMB experience. The DSMB will follow the guidance as outlined in the application and the attached charter unless there is a compelling, unanticipated reason to deviate from these rules. Data regarding the primary outcome (hospitalization) will be reported to the DSMB continuously, consistent with continuous study monitoring principles. The DSMB may recommend stopping the trial early only for safety, following these guidelines:

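### Low blood pressure managed only by changing study drug falls outside both hypotension safety endpoints in 3.3, and no between-arm comparison of such episodes is specified

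*Combined protocol and SAP*

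**What the plan says.** The safety part of the secondary endpoints (3.3) has two hypotension items. The first is "Compare daily hypotensive episodes (MAP < 65 mmHg) prompting intervention (indicated by a fluid bolus" of 500 mL or more, so a vasopressor without a bolus does not qualify. The second is "Hypotensive episodes requiring intervention (vasopressors or fluid bolus"), with no MAP threshold and no bolus volume. Neither counts a low MAP by itself, and neither names a change of study drug as an intervention.

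Section 18.2 sets the response to related events. For serious events (SAEs), "SAEs determined to be probably or definitely related will prompt discontinuation of study drug". For other AEs, "AEs determined to be probably or definitely related with prompt a) decrease in study drug from twice a day to once a day"; the drug is stopped if it is already given once daily, or at the investigator's discretion.

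The continuous DSMB reporting in 18.2 uses the same kind of condition as 3.3: "Cardiovascular events (need for vasoactive drugs or fluids for hypotension), and respiratory events". The list of study outcomes in 18.2 that need not be reported as AEs has the same cardiovascular wording. Those outcomes "are exempt from adverse event reporting unless the investigator deems the event to be related to the study procedures (or of uncertain relationship") or the event leads to discontinuation of study procedures.

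Section 3.4 explains why hypotension is an endpoint at all: patients may be at raised risk of it, "so we will systematically track these measured instead of relying upon adverse event reporting which introduces the potential for bias".

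**The concern.** The endpoints define an episode by two particular treatments, while the protocol's own written response to a related event is a third one. A patient with a MAP of 60 mmHg whose study drug is reduced or stopped, and who gets no bolus and no vasopressor, has been acted on under 18.2 and has no event under 3.3. That leaves the episode to AE reporting, the route 3.4 does not want to rely on.

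Hypotension is a known risk of losartan (13.1), and 8.4 expects a fall of 6-8 mmHg. Section 8.3 excludes a patient whose latest MAP is below 65 mmHg whether or not it was treated, so the protocol already treats that value as meaningful without an intervention. At stake is whether the comparison of hypotension between arms is complete.

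**Working it through.** **The plan's own figures.** The documents give no hypotension rate, no share of episodes managed by study-drug change, and no power for this endpoint. The only power statement (15.2) concerns the P/F ratio. With 100 per arm and two-sided 0.05 (alpha is not stated, so this is assumed), SE = 125 × √(2/100) = 17.68, and power = Φ(50/17.68 − 1.96) = Φ(0.87) = 0.807. This agrees with the stated figure of more than 0.8. The same n and alpha are used below.

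**Which episodes are counted.**

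| Response to MAP below 65 mmHg | First endpoint | Second endpoint | Continuous DSMB report |
|---|---|---|---|
| Bolus of 500 mL or more | yes | yes | yes |
| Vasopressor only | no | yes | yes |
| Study drug reduced or stopped only | no | no | no |
| None | no | no | no |

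**Direction.** Let pL and pP be the true proportions with an episode, and fL and fP the shares that escape counting.

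- Counted difference = pL(1 − fL) − pP(1 − fP). It is below the true difference when pL·fL > pP·fP. If losartan raises hypotension, this holds whenever the escaping share is the same in both arms or larger on losartan. At 15% v 5% it fails only if the placebo share is at least three times the losartan share.
- Counted risk ratio = (pL/pP) × (1 − fL)/(1 − fP). It moves toward 1 only if fL > fP.

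**Illustration (all rates and shares assumed).** In case A, a share f of the excess losartan episodes escapes and no placebo episode does: the counted losartan rate is pP + (pL − pP)(1 − f). In case B, the same share f of all episodes escapes in each arm.

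Power = Φ{[d − 1.96√(2p̄(1 − p̄)/n)] / √([pL(1 − pL) + pP(1 − pP)]/n)}, with n = 100 per arm, d the difference and p̄ the mean of the two rates.

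- 15% v 5%: (0.10 − 0.0832)/0.0418 = 0.40, power 0.66.
- 10% v 5%: (0.05 − 0.0730)/0.0371 = −0.62, power 0.27.
- 7.5% v 2.5%: (0.05 − 0.0604)/0.0306 = −0.34, power 0.37.

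| True rates | Case | f | Counted rates | Difference (points) | Risk ratio | Power |
|---|---|---|---|---|---|---|
| 15% v 5% | all counted | 0 | 15% v 5% | 10 | 3.0 | 0.66 |
| | A | 0.25 | 12.5% v 5% | 7.5 | 2.5 | 0.47 |
| | A | 0.5 | 10% v 5% | 5 | 2.0 | 0.27 |
| | B | 0.25 | 11.25% v 3.75% | 7.5 | 3.0 | 0.52 |
| | B | 0.5 | 7.5% v 2.5% | 5 | 3.0 | 0.37 |
| 20% v 10% | all counted | 0 | 20% v 10% | 10 | 2.0 | 0.51 |
| | A | 0.5 | 15% v 10% | 5 | 1.5 | 0.19 |
| | B | 0.5 | 10% v 5% | 5 | 2.0 | 0.27 |

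The normal approximation is rough at the lowest rates (2.5% of 100 is 2.5 patients), so read these as orders of magnitude.

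**The case against.** Four points can be made for the plan.

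1. *The episodes are not lost.* The 18.2 response starts only once an AE has been judged probably or definitely related, so an episode handled that way is an identified AE with severity and timing recorded. The reporting exemption covers only hypotension needing vasoactive drugs or fluids, and lapses for related events. Daily vital signs and study-drug timing are collected (1.6), 13.1 promises the DSMB assessments of new hypotension, and daily SOFA is a secondary endpoint. This stands: a reader might infer that such hypotension disappears from the safety data, and it does not. What remains is narrower. Section 15 specifies no between-arm analysis of AEs. The guideline in 18.3 compares overall SAE rates, which would not isolate these episodes or include non-serious ones. Section 13.1 does not define an episode, and SOFA is not a count of hypotension.

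2. *The bias has no fixed direction by arm.* A reader might infer that harm is understated mainly in the losartan arm. Care teams are blinded (4.6) and the rule applies in both arms, so study drug will also be cut for hypotension on placebo. It is plausible that withdrawing active drug resolves episodes more often than withdrawing placebo, but the documents do not show it. Case B leaves the risk ratio unchanged.

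3. *The share may be small.* Section 18.2 is a general AE rule; nothing says that a drug change replaces fluid, and a patient who has both is counted. With half-lives of 2 hours and 6-9 hours (4.1), stopping the drug acts over hours. A rating of probably related requires that other causes be unlikely, which is demanding in this population. This stands, and it is why no size can be claimed.

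4. *Requiring treatment is a reasonable severity threshold.* True, and a bare MAP endpoint depends on how often pressure is recorded. This argues for keeping the present endpoints, but not against adding to them.

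**Conclusion.** The gap in the definitions is established from the text: hypotension managed by study-drug change alone is outside both endpoints in 3.3 and outside the hypotension item of the continuous DSMB reporting. No between-arm comparison of such episodes is specified, and they are left to the reporting route that 3.4 sets out to avoid.

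If losartan raises hypotension, the counted absolute difference and the power to detect it are reduced in both cases examined. Attenuation of the risk ratio is conditional on a larger share escaping on losartan. The size is unknown and may be small; the rates of 15% v 5% and 20% v 10% and the shares of one quarter and one half are assumptions, with no source in the documents. The point is an inexpensive improvement to the completeness of the safety comparison. It does not show that the existing endpoints are biased in favour of losartan.

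**What to change.** Keep the two existing endpoints and make these additions.

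- In 3.3, add study drug held, reduced or stopped for low blood pressure as a counted intervention component, and record the reason for the change on the case report form.
- In 3.3 and 15.1, add a supportive between-arm comparison of any recorded MAP below 65 mmHg after the first dose, whatever the response.
- Report bolus, vasopressor, study-drug change and MAP alone separately by arm, and give the same table to the DSMB.

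The cost is one added case report form item and two lines of analysis text. The supportive comparison will include some milder episodes, which the component table makes visible. It will also depend on how often pressure is recorded: 4.1 expects several checks a day, but the data list in 1.6 names only vital signs at presentation and daily. The protocol should state which readings are used, by the same rule in both arms. These changes concern what is counted and reported; none alters clinical management.

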- Evidence of bacterial co-infection
- Glasgow coma scale (daily, if available)
- Death (with date, if applicable)
- Study withdrawal, with date and time (if applicable)

- Final outcome follow-ups will be determined through a combination of patient report, electronic medical record review, and review of the social security death index (SSDI).
- All data will be stored in a password protected Redcap database, with customizable tiered access and an audit trail. All protected health information (PHI) will be marked with a PHI tag that will prevent export, so only deidentified data can be exported from the database. Only deidentified data with no PHI will be exported for analysis.
- Nasopharyngeal or oropharyngeal swabs (day 1,4,8,10,15); 30 patients will receive blood draws for pharmacokinetic analysis (day 1, hours 2, 4, and 6) and patients will provide blood samples for RAAS, RNASeq, flow cytometry, and cytokine assays, collected by study personnel or bedside nurse and placed in pre-packaged transport containers to be collected by biosafety-trained transporters, transported and processed to the University of Minnesota's BSL-3 laboratory noted above, and frozen at -80 C until later analysis for local sites. Blood samples will not exceed 30 mL day 1, and will equal ~21-24 mL on days 2, 4, 6, 8, 10, and 15). All

biospecimens will be labeled with a deidentified patient ID number to prevent inadvertent disclosure of PHI. Participants will be given the opportunity to contribute to an optional study using genetic material for future studies of patient-level responses to COVID-19. These samples will likewise be deidentified, but are theoretically identifiable biologic information.

- Cytokine assays will be conducted by [name]'s laboratory at the University of Minnesota
- RAAS pathway assays will be conducted at the Wake Forest Hypertension and Vascular Research Biomarker Analytical Core
- Pharmacokinetics will be conducted at [name]'s Antiviral Pharmacology Laboratory at the University of Nebraska

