# Only to be performed if patient is an inpatient. Otherwise move to Study procedures following discharge

% Nasopharyngeal swabs and blood draws should be collected if local logistical and biosafety procedures allow. Day 1 and 4 and 10 blood and days 1 and 10 NP or OP swabs are preferred if limited.

@ We will attempt to coordinate follow-up clinic visits within 1-2 weeks from hospital discharge to obtain nasopharyngeal and blood biospecimens

& Subject discharged before D7 will be sent home with a pulse oximeter to calculate P/F ratio and a phone call will be made at this time

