Secondary endpoints will be summarized by the sample mean or sample proportion, as appropriate, and compared using the unequal variance two-sample t-test or Chi-square test, as appropriate. Appropriate data transformations will be used to assure that assumptions of all statistical tests are met. Time-to-event endpoints will be summarized by Kaplan-Meier curves and compared using Cox proportional hazards regression. For all endpoints, we will complete secondary analyses comparing for important baseline variables that are unequally distributed between treatment groups. Preplanned subgroup analyses are planned by age (dichotomized at 50 and by decade), history of hypertension, sex, and smoking history, timing of randomization from symptom onset, and respiratory support needed at the time of randomization.

15.2 *Power Analysis:* Assuming a fixed sample size, we analyzed power using a number of assumptions. In general, studies with a similar degree of acute lung injury that we expect in this study have a standard deviation of estimated P/F ratio of 100-125. ARDS trials tend to have smaller SD due to narrowed inclusion criteria, while a single study of H1N1 with a lower severity of illness had a SD of 150. We calculated power for a variety of assumptions. If the SD is 125 or less, we will have >0.8 power to detect a difference in P/F of 50. Differences of less than this are of uncertain clinical significance. This method and outcome has more power than our alternative approach of respiratory SOFA, which is a more crude measure of the estimated P/F ratio.

15.3 **Data Integrity:** The principal investigator will manage oversight of quality control for collected data. Recruitment of subjects will be performed using inclusion/exclusion criteria defined above. Study data will be recorded within a RedCAP database, which is HIPAA compliant, password protected with variable assignable security access and an audit trail consistent with all regulatory requirements for maintenance of clinical trial data. Data summaries and quality control checks will be run routinely.

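### Change in viral load falls by default to an unadjusted t-test with no rule for undetectable swabs, which shrinks any difference toward zero by an amount that depends on the undetectable share

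*Combined protocol and SAP*

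**What the plan says.** Section 3.3 names the endpoint as "Change in viral load (nasopharyngeal or oropharyngeal swab and blood". Section 3.4 gives its purpose: "Changes in viral load are important to assess the theoretical possibility of losartan induced ACE2 expression leading to increased viral entry, propagation, and shedding". It therefore serves as a check for harm.

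Section 1.6 sets the sampling: "Nasopharyngeal or oropharyngeal swabs (day 1,4,8,10,15". The footnote to the table of events in section 5.6 makes collection conditional: "Nasopharyngeal swabs and blood draws should be collected if local logistical and biosafety procedures allow". It prefers the day 1 and day 10 swabs where sampling is limited. Section 6.2 does not count missing research specimens as protocol deviations.

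Section 15.1 has one generic rule. Secondary endpoints are summarised by means or proportions and "compared using the unequal variance two-sample t-test or Chi-square test, as appropriate". It adds: "Appropriate data transformations will be used to assure that assumptions of all statistical tests are met". Covariates enter only in secondary analyses "comparing for important baseline variables that are unequally distributed between treatment groups". Baseline viral load is not named.

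The documents do not state the assay, its lower limit, the scale, the analysis day or days, how an undetectable result is scored, or an expected mean, SD or effect for viral load.

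**The concern.** A quantitative viral assay has a lower limit. Once a patient is undetectable, the recorded change equals the limit minus that patient's baseline, whatever the drug did. Such values say little about treatment and mostly reflect the baseline load. The transformation clause deals with skewness but not with this: a logarithm still needs a substituted value, and the block of tied values remains.

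As more swabs become undetectable, the difference in mean change shrinks toward zero. For an endpoint meant to reveal greater viral propagation or shedding, that error points to reassurance. A real adverse effect could be reported as no difference.

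**Working it through.** **1. The plan's own power figure.** Section 15.2 gives power only for the primary endpoint: difference 50, SD 125, more than 0.8. With 200 patients 1:1 (sections 10.2 and 4.6), there are 100 per arm. The standard error is 125 × √(2/100) = 17.68, 50/17.68 = 2.83, and Φ(2.83 − 1.96) = 0.81. The figure reproduces. There is nothing comparable to reproduce for viral load.

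**2. Assumed scenario A.** None of these inputs is in the documents:
- 100 per arm with paired swabs, two-sided 0.05.
- Baseline mean 5.5 log10, SD 1.5; assay floor 2.0 log10.
- Decline from day 1 of 0.40 log10 per day on placebo and 0.36 on losartan; residual SD 0.8.

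Follow-up SD is √(1.5² + 0.8²) = 1.7. Elapsed times for study days 4, 8 and 10 are 3, 7 and 9 days.

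Share of placebo at the floor, Φ((2.0 − mean)/1.7):
- Day 4: mean 5.5 − 1.2 = 4.3, giving Φ(−1.35) = 9%.
- Day 8: mean 5.5 − 2.8 = 2.7, giving Φ(−0.41) = 34%.
- Day 10: mean 5.5 − 3.6 = 1.9, giving Φ(0.06) = 52%.

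Shrinkage on day 10: with d = (mean − 2.0)/1.7, the floored mean is 2.0 + (mean − 2.0)Φ(d) + 1.7φ(d).
- Placebo (mean 1.90): 2.63.
- Losartan (mean 2.26): 2.82.
- The difference is 0.19 log10 instead of the true 9 × 0.04 = 0.36.

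Power without a floor: the SD of change is 0.8, so the standard error is 0.8 × √(2/100) = 0.113. On day 8, 0.28/0.113 = 2.47 and Φ(0.51) = 0.70. On day 10, 0.36/0.113 = 3.18 and Φ(1.22) = 0.89. The simulation agrees to within its error.

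Simulated power:

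| Study day | Placebo at floor | t-test, no floor | Welch on floored change | ANCOVA on floored values | Baseline-adjusted Tobit |
|---|---|---|---|---|---|
| 4 | 9% | 0.16 | 0.15 | 0.13 | 0.15 |
| 8 | 34% | 0.70 | 0.34 | 0.47 | 0.64 |
| 10 | 52% | 0.92 | 0.29 | 0.54 | 0.77 |

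Repeat runs moved single entries by up to about 0.05. Tobit rejected in about 6% of trials with no effect.

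**3. Assumed scenario B.** 100 per arm, baseline 4 log10 above the limit (SD 1.5), follow-up SD 1.8, correlation 0.4, losartan 0.8 log10 higher. Power without a floor is about 0.86.

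| Placebo undetectable | Welch on floored change | Mann-Whitney on change | Chi-square on detectability | ANCOVA on floored values | Baseline-adjusted Tobit |
|---|---|---|---|---|---|
| 20% | 0.80 | 0.78 | 0.52 | 0.91 | 0.92 |
| 40% | 0.70 | 0.67 | 0.64 | 0.89 | 0.91 |
| 60% | 0.48 | 0.44 | 0.72 | 0.79 | 0.84 |
| 80% | 0.21 | 0.20 | 0.63 | 0.65 | 0.74 |

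With no effect, the floored t-test rejected in 5-6% of trials. A rank test on change does not recover the loss.

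**4. Range.** Seven combinations of SDs and correlation, each with the effect set to give 0.80 power without a floor. Power of the Welch test on floored log10 change:

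| Placebo undetectable | Power |
|---|---|
| 10% | 0.75-0.79 |
| 20% | 0.67-0.76 |
| 40% | 0.46-0.68 |
| 50% | 0.34-0.61 |
| 60% | 0.24-0.51 |
| 70% | 0.15-0.39 |
| 80% | 0.09-0.24 |

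Power falls to half its nominal value (0.40) somewhere between about 45% and 70% undetectable.

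**5. Source of the gain.** The step from Welch to Tobit mixes baseline adjustment with censoring. The share due to adjustment is (ANCOVA − Welch)/(Tobit − Welch):
- Scenario A, day 8: 0.13/0.30 = 43%. Day 10: 0.25/0.48 = 52%.
- Scenario B: 0.11/0.12 = 92% at 20% undetectable, falling to 0.44/0.53 = 83% at 80%.

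**6. Fewer swabs.** With 60 per arm and a 1.0 log10 effect in scenario B, power is about 0.85 without a floor. With 20/40/60/80% undetectable, the floored t-test has 0.77/0.64/0.43/0.18.

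**The case against.** The strongest reply is that section 15.1 does not bind viral load to a t-test on change. It allows proportions with a chi-square test where suitable, and it allows transformations. The proportion detectable is within its wording and beats the floored t-test in scenario B at 60-80% undetectable, though on day 10 of scenario A it reaches only about 0.27. This stands in part: the plan leaves the choice open. But the endpoint is named as a change, which is continuous, and Welch is the default for that. A reader might also infer a t-test on raw copies, where power is close to zero. That is skewness, which the transformation clause covers.

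Three further objections stand:
- Section 3.4 does not speak of slower clearance. That is an interpretation, used here to build scenario A. Higher early shedding might show on day 4, where the floor costs almost nothing.
- One hundred paired swabs per arm is optimistic. Collection is optional by site, and patients discharged early may drop out of the later days. Both the paired number and the undetectable share among those sampled are unknown. Selective missingness could matter more than the floor, and a censored model does not repair it.
- Crediting the whole gain to censoring would be wrong, as step 5 shows.

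**Conclusion.** The concern holds in conditional form. The default analysis has no rule for undetectable results and no baseline adjustment, and a transformation cannot supply either. The t-test on change then understates a difference in the reassuring direction. The loss is negligible at about 10% undetectable. It is roughly half or more at about 35-50% and above in scenario A, and exceeds half only at about 45-70% in the seven other sets.

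A reader might infer that the planned test loses most of its power. The documents do not support that as a general statement, because they give no undetectable share, assay limit or analysis day. Nor do they support a claim of error in a stated figure: no power is given for viral load, and false-positive rates stay near nominal. The primary analysis is untouched. This is a specification gap in one secondary endpoint. It is worth closing because the endpoint looks for harm and the better method uses samples already planned.

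**What to change.** In section 15.1, give viral load its own paragraph:
- Analyse log10 viral load and name the swab day or days for the comparison.
- State the assay limit, and treat undetectable results as left-censored there, by Tobit-type regression or a censored longitudinal mixed model.
- Include the day-1 value and the age stratum as covariates.
- Report the treatment difference with a 95% confidence interval, and the proportion undetectable per arm on each swab day.
- Add an ANCOVA on floored values as a sensitivity analysis.
- Report the number of paired swabs per arm and day.

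The cost is wording and a little programming, with no new patients, samples or visits. The baseline covariate costs nothing. The censored model assumes approximate normality of log10 values below the limit, which the ANCOVA helps to check.
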